9.6. Other Safety Data

9.6.1. Urine Pregnancy Test Results and Outcomes

Urine pregnancy test results by visit as well as any pregnancy outcome information will be listed for all women of child-bearing potential in the Safety Population.

9.6.2. Hepatitis B DNA

Hepatitis B DNA assessments by visit will be listed for all HBcAb-positive patients who were permitted to enter the study and are in the Safety Population.

^{*} Fredericia Formula for QTcF interval = QT interval / (RR interval) $^{1/3}$. QTcF will be calculated by the site and recorded directly on the ECG eCRF page.

10. PHARMACOKINETICS

will provide Study Data Tabulation Model (SDTM) serum study treatment concentration dataset (PC) to Kezar's third-party vendor. Serum study treatment concentration and population PK analysis datasets and associated analyses will be performed by Kezar's third-party vendor and are outside the scope of this SAP.

11. INTERIM ANALYSIS

An IA will be performed when approximately 50% of the randomized patients with Class III/IV +/-V LN have completed or would have completed the primary endpoint assessment at Week 37 and prior to the completion of the target enrollment. This IA will serve the following purposes: (1) futility analysis and (2) a potential sample size increase up to 50% (only for patients with Class III/IV +/-V LN) if the CP for the primary analysis is ≥40% and <80%. The proportion of patients achieving CRR at Week 37 (the primary endpoint), the proportion of patients achieving PRR at Week 37, and mean percentage change from Baseline in UPCR at Week 37 will be evaluated using similar methods as specified in Section 8.2, Section 8.3, and Section 8.4.1. The study may not be stopped early for success based on the IA findings.

11.1. Futility Analysis

The futility boundary using the Lan-DeMets method (O'Brien and Fleming, 1979; DeMets and Gordon Lan, 2014) is non-binding and is shown in Table 6. The calculation was performed using The futility boundary of Δ =5.4% (4.7% CP at the observed value) will be assessed for the pairwise comparisons of zetomipzomib and placebo using an Intersection-Union approach. In this approach, futility will be declared if both $\Delta 1 \le 5.4\%$ and $\Delta 2 \le 5.4\%$ are true. Otherwise, futility will not be declared if either $\Delta 1 > 5.4\%$ or $\Delta 2 > 5.4\%$ is true. Here, $\Delta 1$ and $\Delta 2$ are pairwise differences in CRR at Week 37 between zetomipzomib 30 mg and pooled placebo and between zetomipzomib 60 mg and pooled placebo, respectively. A decision by the Sponsor to stop the study for futility or to continue as planned will be reached after careful review of the data by the IDMC.

Table 6: Futility Boundary

Information Fraction	Cumulative β Spent at final analysis	Futility Boundary for Treatment Difference (Δ) in CRR at Week 37
50% randomized patients with Class III/IV +/-V LN	0.19786 (80.2% power)	5.4% (CP at the observed value according to =4.7%)

CP=conditional power; CRR=complete renal response; IA=interim analysis; LN=lupus nephritis.

11.2. Potential Sample Size Re-estimation

The (Mehta and Pocock, 2011) methods will be used for potential sample size re-estimation (SSR). The IA may result in a sample size increase of up to 50% (only for patients with Class III/IV +/-V LN) if CP is ≥40% and <80% (defined as the "promising zone"). Sample size can stay the same or increase based on the results of this analysis, but it cannot be decreased. Using these methods, the type I error rate will be preserved and will not be inflated. If conditional power is between 40% and 50% then the Cui, Hung, and Wang statistic (Cui et al., 1999) will be used for the final analysis to preserve type-I error rate.

Simulations (10,000) were performed for illustration purposes for a treatment difference of Δ =20% in CRR at Week 37. It is worth noting that, at the current planned sample size (83 per treatment group or 166 in a 2-treatment comparison), Δ =20% corresponds to 80% power, while

power for a smaller Δ will be lower (ie, power for Δ =15% is around 51%). The simulation results are summarized in Table 7.

Table 7: Simulation Results for Sample Size Adjustment Based on Interim Analysis Data

Effect Size in CRR at Week 37	Conditional Power	Simulation Results (10,000 Simulations)	Sample Size Increase (only for patients with Class III/IV +/-V LN)
Δ=20%	<40%	23.3%	No
(40% versus 20%)	40% to <80% a	20.6%	Yes
	≥80%	56.1%	No

CRR=complete renal response; LN=lupus nephritis

Calculations will be performed separately for both treatment comparisons (zetomipzomib 60 mg vs pooled placebo and zetomipzomib 30 mg vs pooled placebo) and the following SSR rules which are designed to ensure at least one treatment comparison will have 80% power will be applied in the following order based on IA results:

- 1. Do not increase planned sample size if CP is <40% and the futility stopping rule is not met for both treatment comparisons.
- 2. Do not increase planned sample size if CP ≥80% is met for at least one treatment comparison.
- 3. Increase sample size if 40% ≤ CP <80% for at least one of the two treatment comparisons. For the treatment comparison with the higher CP, the number of patients will be increased to the sample size needed to achieve CP of 80% or increased by 50%, whichever is smaller. The number of patients for the other treatment comparison will be increased by the same amount.

The conditional power is calculated assuming the observed effect size at the IA is the true effect size. The calculation is based on B-value (Lan and Wittes, 1988). Let D_I denote the number of patients assessed for the primary endpoint at the IA and D_2 denote the total number of patients for the final comparison at end of study. The information fraction for the conditional power calculation is

$$t = D1/D2$$
.

Let Z_t denote the quantile of the normal distribution associated with the CMH test statistic at the IA. The B-value at the IA is calculated as:

$$\mathrm{B}(\mathrm{t}) = \mathrm{Z}_{\mathrm{t}} \sqrt{t}$$

When data are monitored at t, B(t) is observed, and the conditional power assuming the trend indicated by the interim data is calculated as

$$CP_t = 1 - \Phi \left\{ \frac{z_{0.975} - \frac{B(t)}{t}}{\sqrt{1-t}} \right\},$$

where $\Phi(\cdot)$ is the standard normal cumulative density function.

^a The "promising zone". For simulation purposes, a lower bound of 40% conditional power was chosen to consider for sample size increase. The simulations were performed using (Chen et al., 2004).

Kezar Life Sciences, Inc. KZR-616-202

Statistical Analysis Plan, Version 1.0 Date Issued: 24Jul2024

The exact formula for calculating sample size will not be available to the blinded team in order to prevent back-calculation of the treatment effect.

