4.2. Sample Size

A sample size of 249 patients with Class III/IV +/-V LN or 83 per treatment group (randomized in a 2:1:2:1 ratio for zetomipzomib 30 mg: placebo: zetomipzomib 60 mg: placebo) will have 80% power to detect a 20% difference (40% versus 20%) in CRR between zetomipzomib and placebo at Week 37 (9 months), using a 2-group binomial test (for pooled estimate of variance) with a 0.05 2-sided α level. The assumption of 20% for CRR in the placebo group was made based on the evaluation of relevant published data (Furie et al., 2020; Rovin et al., 2021).

The sample size calculation is intended for pairwise comparisons for zetomipzomib 60 mg versus the pooled placebo group and for zetomipzomib 30 mg versus the pooled placebo group, respectively. There is no statistical comparison between the 2 zetomipzomib dose groups. This sample size also reflects a planned IA for futility when approximately 50% of the randomized patients with Class III/IV +/-V LN have or would have completed the Week 37 visit with the primary endpoint assessment and prior to the completion of the target study enrollment. Based on the IA findings, sample size (for patients with Class III/IV +/-V LN only) may be increased up to 50%; see Section 11.2 for details.

In addition to the 249 patients with Class III/IV +/-V LN, the study will also enroll up to 30 patients with pure Class V LN across the 3 treatment groups, for a total of up to 279 patients. The 30 patients with pure Class V LN were not included in the power calculation, as well as the assessments for type 1 error and multiplicity.

Approximately 214 sites from ~21 countries worldwide are planned to participate in this study.

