8.1. Controlling for Type I Error

Formal statistical tests are planned for the primary and the following key secondary efficacy endpoints. The analyses will be performed based on patients in the ITT Population with Class III/IV+/- V LN only. Patients with pure Class V LN will not be included in the analyses involving hypothesis testing of the following endpoints.

Primary endpoint

• CRR at Week 37

Key secondary endpoints

- CRR at Week 53
- PRR at Week 37
- PRR at Week 53
- CRR at Week 25
- PRR at Week 25

The testing sequence will be performed independently for each zetomipzomib treatment group versus placebo (pooled).

Analysis of the primary endpoint will involve three pairwise comparisons:

- zetomipzomib 60 mg vs placebo
- zetomipzomib 30 mg vs placebo
- [(zetomipzomib 30 mg + zetomipzomib 60 mg) /2] vs placebo

The above treatment comparisons can be tested under the following hypotheses:

- Null hypothesis H₀: P0=P1=P2=0.20
- Alternative hypothesis (a): P1=P2=0.40, P0=0.20
- Alternative hypothesis (b): P1=0.20, P2=0.40, P0=0.20

where P0, P1 and P2 are the true CRR at Week 37 for placebo, and 2 zetomipzomib doses (30 mg and 60 mg), respectively.

Each of the three pairwise comparisons above are assessed at the 2-sided α =0.05 level. As such, the overall Type 1 error rate across the three comparisons will become higher but controlled at the 2-sided level of 0.096716.

For each of the three pairwise comparisons above, a family-wise type 1 error rate at the α =0.05 level (2-sided) level will be used for the analysis of the primary and 5 key secondary endpoints starting from the primary endpoint, so that statistical significance for any of the 5 key secondary endpoints can only be declared if the same comparison on the primary endpoint (primary estimand) achieves statistical significance at the 2 sided α =0.05 level. The Hochberg step-up method (Hochberg, 1988) will be applied to adjust for hypothesis testing of each pairwise comparison on all 5 key secondary endpoints and maintain the overall type I error rate at the α =0.05 level for each of the pairwise comparisons. Results from all statistical analyses, regardless of the level of significance, will be provided. Results that are statistically significant according to the Hochberg method will be indicated with a "*" next to the significant p-value.

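### SAP 11.2 states that type I error is preserved, but a sample size increase also enlarges the dose with lower conditional power, and the adjusted statistic is named only for 40% to 50%, without saying whose conditional power counts

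*SAP*

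**What the plan says.** SAP 11.2 computes CP separately for 60 mg and for 30 mg, each against pooled placebo. If neither reaches 80% and at least one lies from 40% up to 80%, rule 3 enlarges the trial. The comparison with the higher CP is raised to the size that gives 80% CP, or by 50% if that is smaller. Then: "The number of patients for the other treatment comparison will be increased by the same amount". No condition is placed on that other comparison's CP.

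On the final test, the section says "If conditional power is between 40% and 50% then the Cui, Hung, and Wang statistic" is to be used, and gives preservation of type I error as the reason. It also makes a general claim: "Using these methods, the type I error rate will be preserved and will not be inflated". Protocol 10.9 makes a similar claim and ties it to CP from 40% up to 80%.

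SAP 8.1 tests three primary comparisons, the third being the average of the two doses against placebo. "Each of the three pairwise comparisons above are assessed at the 2-sided" 0.05 level, and an overall error of 0.096716 is accepted. SAP 8.2.2 and Table 5 name the stratified CMH test for all three. SAP 11.2 gives no CP for the pooled-dose comparison and does not say whether CHW replaces CMH for it after an increase.

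**The concern.** The promising-zone argument allows the ordinary test after an increase only when the comparison being tested had a sufficiently favourable interim result. With a low interim result, added patients dilute a poor first stage and raise the chance of a false positive. The SAP accepts this by switching to CHW below 50%. Yet rule 3 can enlarge a dose whose CP is below 40%, the SAP's own no-increase zone, and no adjusted statistic is named there.

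What is at stake is the 0.05 per comparison. The plan already accepts 0.096716 across the three comparisons, so this is the remaining control, and it is also the gate to the five key secondary endpoints. There is a practical risk too: after an increase, two programmers could defensibly choose different final statistics.

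**Working it through.** **Inputs.** SAP 4.2: "A sample size of 249 patients with Class III/IV +/-V LN or 83 per treatment group", "80% power to detect a 20% difference (40% versus 20%) in CRR between zetomipzomib and placebo", "with a 0.05 2-sided α level", and a "2:1:2:1 ratio for zetomipzomib 30 mg: placebo: zetomipzomib 60 mg: placebo". After pooling placebo the allocation is 1:1:1, so the two dose statistics share a control and have null correlation 0.5. SAP 11: interim at about half the patients, so t = 0.5 and 41.5 per group. SAP 11.2: cap of 1.5 × 83 = 124.5 per group, and CP by the B-value formula at the observed trend.

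**The plan's own figures.**
- Power for 40% against 20% with 83 per group: pooled SE = √(2 × 0.3 × 0.7/83) = 0.0711; unpooled SE = √((0.24 + 0.16)/83) = 0.0694; Φ[(0.20 − 1.96 × 0.0711)/0.0694] = 80.9%. The SAP says 80%.
- Overall error, taking the pooled-dose statistic as (Z30 + Z60)/√3: 0.0967. The SAP says 0.096716.
- SAP Table 7 zones: 23.5% / 19.6% / 56.9%. The SAP gives 23.3% / 20.6% / 56.1%.

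**CP cut-offs.** At t = 0.5, CP = c corresponds to z = √0.5 × [1.96 − √0.5 × Φ⁻¹(1 − c)]. This gives z = 1.259 (40%), 1.386 (50%) and 1.807 (80%).

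**Conditional error of the ordinary statistic.** With interim value z and final size N\* per group, it is 1 − Φ[(1.96√N\* − z√41.5)/√(N\* − 41.5)]. CHW keeps it at the value for N\* = 83.

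| Own CP | z | N\* = 83 | N\* = 124.5 |
|---|---|---|---|
| 10% | 0.745 | 0.0213 | 0.0305 |
| 20% | 0.965 | 0.0354 | 0.0429 |

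At the full 50% increase the two columns are equal at CP of about 41%. Above that the ordinary statistic is safe; below it, error rises.

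**Simulated error for 30 mg, no true 30 mg effect.** Normal model, all three SAP rules applied. Drift is the expected final z for 60 mg at the planned size; 0.20/0.0711 = 2.81 is the SAP's alternative (b).

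| | Drift 2.0 | Drift 2.81 |
|---|---|---|
| Trial enlarged | 22% | 20% |
| Of those, 30 mg CP below 40% | 89% | 95% |
| False positives in those runs, ordinary / CHW | 1.24% / 0.88% | 0.92% / 0.62% |

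Over all trials, the one-sided 30 mg error depends on how the CHW sentence is read:
- Each comparison's own CP decides: about 2.55% (two-sided 5.06% to 5.10%).
- The triggering comparison's CP decides for all: about 2.53% to 2.54%.
- CHW after any increase: 2.50% (5.00%).

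The sizes agree. At drift 2.0, 0.197 of all trials are enlarged with 30 mg CP below 40%, and 0.197 × (1.24 − 0.88) = 0.07 points. The net excess is slightly smaller because the ordinary statistic is slightly conservative where 30 mg's own CP is 50% or more.

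**Global null (all rates 20%).** The trial is enlarged in about 11% of runs. Each dose is at about 2.5% one-sided, the pooled-dose comparison at 2.50%, and the overall two-sided error at about 9.6% to 9.7%. There is no material inflation.

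**The case against.** The case for leaving the text alone is substantial.

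- SAP 8.1 states one null hypothesis, with all three rates equal, and under it the preservation claim holds. This stands. The excess appears only when one dose works and the other does not, a pattern SAP 8.1 lists as an alternative. For the 30 mg test, however, that is a true null, and SAP 11.2 does not limit its claim to the global null.
- The excess is about 0.05 points one-sided. In a binomial check with 60 mg at 35%, a fixed design with no adaptation already gives 2.55% from discreteness, against 2.62% with the sample size rule. This stands, and it limits the point to a small correction.
- A reader might take 1.24% against 0.88% as a 40% rise in the trial's error rate. It is not: it describes only the roughly one trial in five that is enlarged with 30 mg CP below 40%.
- A reader might infer that CMH is certainly the final test for a dose below 40%. The SAP does not say so. The CHW sentence could be read as letting the triggering CP decide for the whole analysis. That reading shrinks the excess but does not remove it.
- A reader might infer that the pooled-dose comparison has no rule at all. It has one: SAP 8.2.2 and Table 5 name the CMH test. What is missing is narrower, and no inflation is shown for it under the global null.

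**Conclusion.** The point holds in a limited form. The general statement of preserved type I error in SAP 11.2 is not met for the lower-CP dose when only the other dose works: about 2.55% one-sided instead of 2.50%, or 2.53% to 2.54% on the more favourable reading. The text also leaves open whose CP selects the statistic and what is used for the pooled doses after an increase. The documents do not support a conclusion that the trial's error rate is materially inflated, or that the stated 0.096716 is exceeded under the SAP's null.

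The figures rest on an interim at exactly half the information, a normal approximation, a shared placebo group, the 50% cap, and the increase being set by the higher CP as rule 3 states. The change is worth making because the plan claims this property and one sentence secures it.

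**What to change.** Replace the 40% to 50% sentence in SAP 11.2, before the interim analysis, with: *If the sample size is increased, the Cui-Hung-Wang statistic with the pre-planned weights is used for all three primary comparisons.* In simulation this returns each true-null dose comparison to 2.50% one-sided in every scenario tested, and it settles the pooled-dose statistic.

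A narrower version also holds the two dose comparisons at or below 2.5%: use CHW for any dose comparison whose own CP is below 50%, including below 40%, and state CHW for the pooled-dose comparison as well.

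The cost is one SAP sentence and a power change of under 1 point: from 82.9% to 82.7% per dose under alternative (a), and from 39.5% to 38.8% for the pooled doses when only 60 mg works. If the sponsor prefers the present rule, the SAP should say whose CP decides and replace the general claim with simulated error rates for the exact rule, including the case where one dose works and the other does not.

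### The printed power of about 51% for a 15-point difference does not follow from the stated test and placebo rate (58%), and the SAP describes a capped conditional-power target as 80% power

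*SAP*

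**What the plan says.** SAP 4.2 and Protocol 10.3 size the trial at 83 Class III/IV ±V patients per group for 40% versus 20% CRR at Week 37, two-sided 0.05, "using a 2-group binomial test (for pooled estimate of variance"). The placebo rate of 20% is the only one given.

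SAP 11.2 and Protocol 10.9.1 repeat that a 20-point difference has 80% power at this size, and give for a smaller difference "15% is around 51%). The simulation results are summarized in Table 7". Neither place prints the two response rates or a different test. SAP Table 6 gives the design's power after the futility look as "0.19786 (80.2% power").

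SAP 11.2, but not the Protocol, introduces the "SSR rules which are designed to ensure at least one treatment comparison will have 80% power will be applied". Under those rules, nothing is added when conditional power (CP) is below 40%. In the promising zone, the sample size for the better-performing dose is "increased to the sample size needed to achieve CP of 80% or increased by 50%, whichever is smaller". On how CP is obtained: "The conditional power is calculated assuming the observed effect size at the IA is the true effect size".

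**The concern.** The two powers stand in one sentence and appear to describe the same test at the same sample size, but the second does not follow from the basis that gives the first. A reader using this sentence to judge how the trial would fare at 15 points would take the chance of success to be about a coin flip.

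The re-estimation clause raises a different problem. Power is a property of the design under an assumed true effect. CP at the observed trend depends on the interim estimate. A rule that targets the second and stops at a cap does not secure 80% of either, so the clause credits the adaptation with a property it lacks.

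**Working it through.** **Power at 83 per group.** Inputs: n = 83, critical value 1.96, placebo 20% (SAP 4.2). The 15-point rates are not printed, so I take 35% versus 20%.

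Power = Φ[(Δ − 1.96·s0)/s1], with s0 = √(2p̄(1−p̄)/n) and s1 = √([p1(1−p1) + p0(1−p0)]/n).

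- 40% versus 20%: p̄ = 0.30, s0 = 0.07114, s1 = 0.06942. (0.20 − 0.13942)/0.06942 = 0.873, so power is **80.9%**. The plan's 80% is reproduced.
- 35% versus 20%: p̄ = 0.275, s0 = 0.06931, s1 = 0.06833. (0.15 − 0.13585)/0.06833 = 0.207, so power is **58.2%**. The plan's 51% is not reproduced.

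Exact enumeration of the pooled test gives 58.6% at 15 points, unpooled variance 59.3%, and the arcsine method 58.8%. If the futility stop is applied (interim difference must exceed 5.4 points at half information), the pooled test gives 79.1% at 20 points and 56.1% at 15.

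**What comes close to 51%.**

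| Basis | 15 points | 20 points |
|---|---|---|
| Stated test, 20% placebo | 58.2% | 80.9% |
| Same, with futility stop | 56.1% | 79.1% |
| Continuity-corrected, 20% placebo | 51.2% | 75.8% |
| Fisher exact, 20% placebo | 52.1% | 76.7% |
| Stated test, 30% placebo | 51.5% | 75.3% |

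The corrected row subtracts 1/n = 0.01205 from Δ: (0.15 − 0.01205 − 0.13585)/0.06833 = 0.031, giving 51.2%. Each of the last three rows loses the 80% printed beside the 51%.

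**Conditional power after a capped increase.** SAP 11.2's formula, with B(t)/t = Z/√t, is CP = Φ[(Z/√t − 1.96)/√(1−t)]. The interim look is placed as follows: "An IA will be performed when approximately 50% of the randomized patients" have reached Week 37, so I take t = 0.5. Raising N by 50% leaves Z unchanged and makes t = 0.5/1.5 = 1/3.

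- Interim CP 40% means Z = 1.259. After the increase: Φ[(1.259/√(1/3) − 1.96)/√(2/3)] = Φ[(2.181 − 1.960)/0.8165] = Φ(0.271) = **60.7%**.
- Interim CP 50% means Z = 1.386: Φ[(2.400 − 1.960)/0.8165] = Φ(0.539) = **70.5%**.
- CP of 80% after the full 50% needs Z of about 1.528, which is an interim CP of **61.2%**.

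With t anywhere from 0.40 to 0.60, the first figure runs from 59.2% to 62.4%, and the 80% threshold is reached from an interim CP of 60.8% to 61.6%. For the whole stretch from 40% to about 61%, the cap therefore stops the rule short of its own conditional target.

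**Unconditional power for at least one dose** (simulation of the rule, no futility stop): 93% if both doses are at 40% and 83% if only one is; 78% if both are at 35% and 62% if only one is. A separate simulation with the futility stop gave 77% and 60% for the two 35% cases.

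**The case against.** The 15-point rates are unprinted, so calling 51% wrong depends on reading the difference as 35% versus 20%. If the active rate is held at 40% instead (40% versus 25%) and the futility stop is treated as binding, power is 52.3%, beside 79.1% for 40% versus 20%. Both are close to the printed figures. This stands as a caution: a reader might infer that the sentence must mix two different tests, and the documents do not prove that. The route does, however, need a 25% placebo rate and a binding bound, where SAP 4.2 states 20% and SAP 11.1 calls the bound non-binding.

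The plan's other figures are not an exact fit to the pooled test either. Table 6's 80.2% is recovered with unpooled variance plus the futility bound; the pooled test with the bound gives 79.1%. Table 7 prints 23.3/20.6/56.1%. The CP formula gives 22.9/19.4/57.8% at 80.9% power and 26.7/20.3/52.9% at 75.8%. The uncorrected basis is clearly nearer, but the gap in the last cell exceeds the simulation error of about 0.5 points.

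On re-estimation, the SAP describes a design aim rather than giving a guarantee, and it prints the CP target, the cap and the 40% floor directly below. A careful reader can see the limits. That is a good reason to treat the clause as a wording fault, but it still names the wrong quantity.

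**Conclusion.** Both parts hold as minor corrections. On the stated test, level and placebo rate, the 15-point power is about 58% (about 56% with the futility stop), so the printed figure is about 7 points low (about 5 with the stop). This assumes 35% versus 20%. The re-estimation rule aims at 80% conditional power for the leading dose. When the cap binds, it leaves that dose at about 61% to 80%, assuming an information fraction near 0.5.

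Two stronger readings should be resisted. A reader might infer that the trial is undersized. It is not on this evidence: the 80% behind the 249 patients reproduces, the 51% is offered as an illustration and errs low, and no boundary, CP threshold or re-estimation rule uses it. A reader might also infer that the adaptation fails at the planned effect. It does not: at 40% versus 20%, power for at least one dose is above 80% whether one dose or both are effective (83% and 93%, no futility stop). The clause fails at 35% versus 20%, an effect for which the trial was not sized.

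**What to change.** 1. In SAP 11.2 and Protocol 10.9.1, restate the 15-point power as about 58% for 35% versus 20% (about 56% with the futility stop applied). Alternatively, keep 51% and print the two rates and the test that produce it.
2. In SAP 11.2, describe the rules as aiming for 80% conditional power under the observed trend for the leading dose, subject to the 50% cap.

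The cost is wording in two sections. Sample size, futility boundary, promising zone and re-estimation rules stay as they are. The Protocol sentence can wait for the next amendment if the SAP is corrected first.
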